## 2.2. Hypothesis

As this is an exploratory study, no formal hypothesis testing will be performed.

## 3. STUDY DESIGN AND RATIONALE

### 3.1. Overview of Study Design

This is a multicenter, interventional, randomized, partially-blind, placebo-controlled, two-part study to assess the efficacy, safety, and pharmacokinetics of treatment with two doses of JNJ-56136379 administered as monotherapy and in combination with NA (either ETV or TDF as per local practice) in HBeAg-positive and -negative CHB-infected subjects. Subjects who completed the initial 24 weeks of treatment with a virologic response by Week 20 (HBV DNA  $<200$  IU/mL of the HBV DNA assay) and without experiencing any safety concerns precluding continued study drug treatment as determined by the investigator, will continue study drugs up to 48 weeks in a treatment extension phase.

The study will initially consist of 2 parts, Part A and Part B. For each part, a sample size of 110 subjects is targeted who will receive JNJ-56136379 at two dose levels as monotherapy or in combination with an NA. Additional parts may be added through a protocol amendment based on emerging data.

Each part will consist of 2 types of CHB-infected subject populations: (1) subjects who are currently not being treated for their CHB infection (including CHB treatment-naïve subjects) and (2) subjects virologically suppressed by current NA treatment (either ETV or TDF as per local practice).

**Part A:**

Approximately 70 subjects who are currently not being treated for their CHB infection will be randomized in a 3:1:3 ratio to receive one of the following treatments:

- Treatment Arm 1: JNJ-56136379 (N=30) (open-label)

After full recruitment, this treatment arm was discontinued early per Protocol Amendment 4. All subjects were to stop further dosing with JNJ-56136379 75 mg, start treatment with NA, and enter the post-treatment follow-up phase (Schedule 1).

- Treatment Arm 2: Placebo + NA (ETV or TDF) (N=10)
- Treatment Arm 3: JNJ-56136379 + NA (ETV or TDF) (N=30)

At the same time, approximately 40 subjects who are virologically suppressed by current NA treatment will be randomized in a 1:3 ratio to receive one of the following treatments:

- Treatment Arm 4: Placebo + NA (ETV or TDF) (N=10)
- Treatment Arm 5: JNJ-56136379 + NA (ETV or TDF) (N=30)

**Part B:**

Part B (ie, Treatment Arms 6 to 10) will follow the same format as Part A, with a different dose of JNJ-56136379 (see [Figure 1](#)).

Randomization in each part will be stratified by:

- HBeAg status at screening (positive versus negative);
- HBsAg level at screening ( $\geq 10,000$  versus  $< 10,000$  IU/mL for HBeAg-positive subjects currently not being treated and  $\geq 1,000$  versus  $< 1,000$  IU/mL for all other subjects).

The aim is to have approximately 40% HBeAg-positive subjects who are currently not being treated and 30% HBeAg-positive virologically suppressed subjects. To this end, enrollment of HBeAg-negative subjects may be capped at 60% in subjects who are currently not being treated and at 70% in virologically suppressed subjects.

A DRC will be established for this study (see Section [11.12](#)) and will monitor safety and efficacy data in an unblinded manner on a regular basis throughout the study.

Part A will start first and will evaluate a 75-mg once-daily dose of JNJ-56136379. The dose to be administered in Part B will be 250 mg given once daily. This dose has been selected by the sponsor, in agreement with the DRC, based on all safety, PK, and antiviral activity data available following completion of the highest JNJ-56136379 dose group (who received 250 mg once

daily) in the Phase 1 study 56136379HPB1001 in treatment-naïve CHB-infected subjects treated for 28 days. (For a rationale on dose selection refer to the Study Design Rationale below.)

Each part of the study will consist of a screening phase (up to 8 weeks), a treatment phase (24 weeks or 48 weeks, depending on treatment response), and a post-treatment follow-up phase (24 weeks or 48 weeks, depending on treatment response). For an overview of the study design, see [Figure 1](#).

All subjects are planned to be treated for at least 24 weeks. Following this initial treatment period, subjects who completed the 24-week treatment period with virologic response by Week 20 (HBV DNA <200 IU/mL of the HBV DNA assay) and without experiencing any safety concerns precluding continued study drug treatment as determined by the investigator, will continue study drugs up to 48 weeks in a treatment extension phase. Subjects enrolled in the study before the Amendment 2 came into effect will need to consent separately for participation in the extension phase. Subjects choosing not to participate in the extension phase will complete their assigned 24-week treatment after which they will enter the 24-week follow-up period. Subjects who are enrolled after the Amendment 2 came into effect will consent to the possible treatment extension by signing the ICF at the start of the study.

Per Protocol Amendment 4, subjects in the JNJ-56136379 250 mg monotherapy arm (Treatment Arm 6) who are eligible for treatment extension, based on the treatment extension criteria assessed at Week 20 (see Section [6.1](#)), will receive JNJ-56136379 in combination with NA treatment from Week 24 to Week 48. In addition, if ≥1 subject in the JNJ-56136379 250 mg monotherapy (Treatment Arm 6) experiences virological breakthrough during the first 24 weeks of treatment, NA treatment will be added to JNJ-56136379 treatment as soon as possible for all remaining subjects (futility rule, see Section [6.2](#)).

For subjects who are not eligible to participate in the treatment extension phase:

- Subjects will be considered to have completed the study treatment if they have completed 24 weeks of study drug administration, after which they will discontinue JNJ-56136379 or placebo treatment. NA treatment (either ETV or TDF as per local practice) should be started (in case of JNJ-56136379 monotherapy, ie, Treatment Arms 1 and 6) or continued (in case NA treatment was part of the assigned study treatment, ie, Treatment Arms 2 to 5 and 7 to 10) as per local treatment guidelines.
- Subjects will be considered to have completed the study if they have completed the assessments of the end of study visit (Follow-up [FU] Week 24 [Schedule 1]).
- For subjects who do not continue or start NA treatment at Week 24, an additional 24-week follow-up (as per local treatment guidelines) by their primary care physician, outside of the study, is recommended after study completion.

For subjects who continue treatment in the extension phase:

- Subjects will be considered to have completed the study treatment if they have completed 48 weeks of study drug administration, after which they will discontinue JNJ-56136379 or placebo treatment. At Week 48:

- Subjects who meet all of the Individual Subject Treatment Completion Criteria (see Section 6.3) will complete all treatment. These subjects will be followed-up until 48 weeks after EOT (Schedule 2). If, during the 48-week follow-up, a subject meets one of the re-treatment criteria described in Section 6.4, NA treatment (ETV or TDF) should be re-started.
- Subjects who do not meet the Individual Subject Treatment Completion Criteria should start (in case of JNJ-56136379 monotherapy, ie, Treatment Arms 1 and 6) or continue (in case NA treatment was part of the assigned study treatment, ie, Treatment Arms 2 to 5 and 7 to 10) NA treatment as per local treatment guidelines. These subjects will be followed-up until 24 weeks after the end of study treatment (Schedule 1).
- Subjects will be considered to have completed the study if they have completed the assessments of the end of study visit (FU Week 24 [Schedule 1] or FU Week 48 [Schedule 2]).
- For subjects who do not meet the Individual Subject Treatment Completion Criteria and do not start or continue NA treatment at Week 48, an additional 24-week follow-up (as per local treatment guidelines) by their primary care physician, outside of the study, is recommended after study completion.

The duration of individual participation will be up to approximately 56 weeks (subjects not eligible to continue treatment in the extension phase), up to 80 weeks (subjects continuing treatment in the extension phase but not meeting the treatment completion criteria), or up to 104 weeks (subjects meeting treatment completion criteria).

Efficacy will be evaluated through different measures (see Section 9.2).

Samples for HBV genome sequence will be taken at the time points indicated in the **TIME AND EVENTS SCHEDULE** (see Section 9.3). Sequencing of baseline samples will be performed by default if HBV DNA levels are within the ranges required for the sequencing assay. The sequencing of samples obtained after baseline may be triggered by the sponsor virologist based on changes in HBV DNA levels observed in each individual subject and the limits of the sequencing assay.

Pharmacokinetic assessments during the study will be performed using a popPK model (see Section 9.4).

Pharmacokinetic/pharmacodynamics relations will be evaluated (see Section 9.5).

The study includes collection of blood samples for exploratory analysis of host blood biomarkers at the host mRNA, protein, and cell level (see Section 9.6).

An optional blood sample for pharmacogenomics (DNA) research can be taken and will only be collected from subjects who consent separately to this component of the study (see Section 9.7).

Patient-reported outcome instruments (EQ-5D-5L, HBQOL, MOS-CFS Cog-R, and SF-36v2) will be used to assess the impact of HBV treatment on subjects (see Section 9.8).

Safety and tolerability, including AEs, laboratory assessments, ECGs, physical examination, and vital signs will be assessed throughout the study from the time that the informed consent form (ICF) is signed until the completion of the last study-related activity (see Section 9.9).

Interim analyses may be performed as indicated in Section 11.11.

The **TIME AND EVENTS SCHEDULE** summarizes the frequency and timing of efficacy, safety, and pharmacokinetic assessments.

[figure not shown]
The study is considered completed with the last visit of the last subject participating in the study.

If a subject discontinues study treatment before the end of the 24-week treatment phase or, if applicable, the 24-week treatment extension phase (ie, Week 48 visit), follow-up assessments should be obtained until 24 weeks after EOT (Schedule 1) unless the subject withdraws consent. NA treatment (either ETV or TDF as per local practice) should be continued or, in case of JNJ-56136379 monotherapy, started at the time of early discontinuation of study treatment as per local treatment guidelines. An additional 24-week follow-up (as per local treatment guidelines), by their primary care physician outside of the study, is recommended after the 24-week follow-up phase in the study (Schedule 1), for subjects who do not continue or start NA treatment after early study treatment discontinuation.

If a subject withdraws before completing the study, the reason for withdrawal is to be documented in the electronic Case Report Form (eCRF) and in the source document. Subjects who withdraw consent will be offered an optional safety follow-up visit.

A liver biopsy substudy may be performed at selected study sites. Patients need to provide consent for the substudy by signing a separate ICF. Refusal to participate in or withdrawal of consent for the substudy does not affect participation in the main study. A liver biopsy will be performed at different time points. The substudy assessments will be described in a separate substudy protocol, which will only be submitted for approval by regulatory authorities (Health Authority/Institutional Review Board (IRB)/Independent Ethics Committee [IEC]) for the selected sites. Results of the liver biopsy substudy will be reported in a separate report.

A diagram of the study design is provided in [Figure 1](#).

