# Date of the Week 24 visit included the EX dataset.

Note: The last phase, whichever it is for a subject, always ends on the day of trial termination (last contact) or the cut-off date in case the data are analysed for an interim or DRC analysis (whichever comes first).

There are two types of follow-up in this study defined (FAOBJ = 'DID THE SUBJECT MEET ALL THE TREATMENT COMPLETION CRITERIA AS PER PROTOCOL?'):

- Treatment free: subjects meeting the criteria mentioned in CTP section 6.3 and therefore subject will start follow-up phase without NA treatment.
- NA follow-up: subjects not meeting the criteria mentioned in CTP section 6.3 and therefore subject will start/continue follow-up phase with NA treatment.

For analyses that require a particular visit, the Time Point Window and Visit Window are defined in the table 2 as below.

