### 5.2.1 Parameter Definitions

The following parameters will be derived as follows:

*Viral breakthrough during 24 weeks of treatment (all subjects), during 48 weeks of treatment (subject with treatment extension) and during NA follow up for all subject who switch to NA-treatment during follow-up:*

HBV virological breakthrough is defined as having a confirmed on-treatment HBV DNA increase by  $>1$  log10 from nadir level (lowest level reached during 24/48 weeks treatment) or a confirmed on-treatment HBV DNA level  $>200$  IU/mL in subjects who had HBV DNA level below the lower limit of quantification (LLOQ) of the HBV DNA assay.

The proportion of subjects with a viral breakthrough is defined as follows:

---

- 0 (No) = subject has not had a viral breakthrough (see definition above) up to the considered time point
- 1 (Yes) = subject has a viral breakthrough at the considered time point or has had a viral breakthrough before (regardless of the HBV DNA result at the considered time point)
- 2 (No: ongoing): subject has not had a viral breakthrough (see definition above) up to the last time point but is still ongoing (only for interim analysis)

Confirmed means that the criterion should be fulfilled at 2 or more consecutive time points or at the last observed time point on-treatment. On-treatment means in the treatment phase, except for the baseline record.

The proportion of subjects with a viral breakthrough during initial 24- or 48-weeks treatment but still on NA Treatment (Yes / No)

Note: For Viral breakthrough during NA follow up, only subject on NA treatment will be include in the denominator.

*Viral relapse* is defined in the follow-up phase as follows:

- 1 (Yes) = viral relapse: confirmed  $\geq 2000$  IU/mL quantifiable.
- 0 (No) = no viral relapse: at least one post-treatment measurement available and not a viral relapse
- 2 (Not applicable) = no post-treatment HBV DNA measurements available
- 3 (No: ongoing) = no viral relapse: at least one post-treatment measurement available and not a viral relapse but still ongoing (only for interim analysis)

Confirmed means that the criterion should be fulfilled at 2 or more consecutive time points or at the last observed time point.

Note: viral relapse will only be assessed for those subjects who at the actual end of treatment have HBV DNA  $< 20$  IU/ml detectable/ undetectable.

*Biochemical relapse* is defined in the follow-up phase as follows:

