## **6. SAFETY EVALUATIONS**

All safety analyses will be performed using the Safety population. All assessments will be analyzed as described in section 2.6. Additionally, the displays will also be presented by analysis phase, analysis period and follow-up type except for the adverse event displays which will be displayed by analysis phase and follow-up type. The planned time points will be considered for time point analysis if applicable.

Safety and tolerability will be assessed by the incidence of treatment emergent-adverse events (TEAEs), physical examinations, vital signs measurements, changes in clinical laboratory parameters (including hematology, blood biochemistry, blood coagulation, and urinalysis), and 12-lead ECGs.

---

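### SAP 2.3 infers NA use in follow-up from the completion criteria, so any subject who misses the criteria and takes no NA is displayed as NA follow-up

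*Protocol*

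**What the plan says.** SAP 2.3 sets the type of follow-up from one form question, "DID THE SUBJECT MEET ALL THE TREATMENT COMPLETION CRITERIA AS PER PROTOCOL". If the answer is yes, the subject is classed as treatment free. The other class is defined as "NA follow-up: subjects not meeting the criteria mentioned in CTP section 6.3 and therefore subject will start/continue follow-up phase with NA treatment". There is no third class, and recorded NA intake plays no part in the rule.

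The protocol treats NA after study treatment as something that should happen, according to local guidelines (Sections 1.3.5, 3.1, 6.1 and 6.3). It also makes provision for subjects in whom it does not happen. The Synopsis and Section 3.1 name three such situations:

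- after the initial treatment period: "For subjects who do not continue or start NA treatment at Week 24, an additional 24-week follow-up";
- after the extension: "For subjects who do not meet the Individual Subject Treatment Completion Criteria and do not start or continue NA treatment at Week 48" (also in Section 10.1);
- after stopping early: "for subjects who do not continue or start NA treatment after early study treatment discontinuation".

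Section 10.2 further allows NA to be stopped along with JNJ-56136379, on the investigator's judgement in consultation with the sponsor.

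The follow-up type is then used as a display factor. SAP 5 analyses all virology and serology by follow-up type, where applicable. SAP 6 says that "the displays will also be presented by analysis phase, analysis period and follow-up type except for the adverse event displays". That exception removes only the analysis period for adverse events, which are still shown by phase and follow-up type. One endpoint has its own restriction (SAP 5.3, Parameter Definitions): "For Viral breakthrough during NA follow up, only subject on NA treatment will be include in the denominator".

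**The concern.** The word therefore in the SAP definition turns a default into a fact. A subject who misses the completion criteria and takes no NA is not treatment free in the SAP's sense, so the only class left is NA follow-up. That subject's post-treatment HBV DNA, HBsAg, ALT and adverse events would then appear under a label saying that they occurred on NA.

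The follow-up tables are where a reader would look for viral control and liver safety after JNJ-56136379 stops, with and without NA cover. Liver enzyme increases are the study's events of special interest (Protocol 11.10). If the NA follow-up column contains subjects without NA, it cannot be read as experience on NA, and off-NA experience outside the treatment-free group has no column of its own.

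**Working it through.** No figure in the plan bears on this point, so the check is mainly a comparison of texts.

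**1. Cross the two facts that matter: criteria met or not, NA taken or not.**

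- Criteria met, no NA: labelled treatment free. Correct.
- Criteria not met, NA taken: labelled NA follow-up. Correct.
- Criteria not met, no NA: labelled NA follow-up. Incorrect. The protocol allows for this cell after Week 24, after Week 48 and after early discontinuation. Week 24 completers and early discontinuers cannot have met Section 6.3, which presupposes 48 weeks of treatment.
- Criteria met, NA re-started later: the label stays treatment free after the re-start. This is a separate and smaller matter.

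**2. Trace the label to the outputs.** HBV DNA and HBsAg summaries carry it through SAP 5. ALT values and toxicity grades carry it through SAP 6. Adverse events, including the liver-enzyme events of special interest, also carry it through SAP 6.

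**3. Check which endpoints are protected.** Viral breakthrough during NA follow-up is limited to subjects on NA by the note quoted above. The note does not say whether on NA means at the event, throughout follow-up, or by the SAP 2.3 label; under the last reading it would exclude nobody. Post-treatment failure during follow-up with NA (SAP 5.3) covers Week 24 completers who were not extended, subjects who missed the Week 48 criteria, and early discontinuers. Reading its breakthrough condition as applying to all three groups, it inherits the same protection.

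**4. Look for a home for off-NA rebound.** Failure with NA requires breakthrough on NA. Failure during treatment-free follow-up requires that the completion criteria were met. A subject off NA without having met the criteria, whose HBV DNA rebounds, satisfies neither definition.

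**5. Size.** Let q be the share of the NA follow-up group that takes no NA.

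- Displayed rate = (1 − q) × on-NA rate + q × off-NA rate
- Bias = displayed rate − on-NA rate = q × (off-NA rate − on-NA rate)

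Neither document gives q, or either rate in follow-up. As an illustration only, assume mean HBV DNA of 1 log10 IU/mL on NA and 5 log10 off NA, a group of 30, everyone off NA at or above 2,000 IU/mL and nobody on NA at that level:

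- q = 0: mean shift 0; share shift 0 points
- q = 1/30: 4 × 1/30 = 0.13 log10; 3.3 points
- q = 3/30: 4 × 3/30 = 0.40 log10; 10 points
- q = 6/30: 4 × 6/30 = 0.80 log10; 20 points

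In a planned control arm of 10, one such subject is 1/10 = 10 points. With the control arms pooled over Parts A and B within a population, as in the main layout of SAP 2.6, it is 1/20 = 5 points. Both assume that the whole arm is in this follow-up type.

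**The case against.** The best case against has four parts.

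**NA is the rule, not the exception.** The protocol says repeatedly that NA should be started or continued, and the study dispenses it in Schedule 1. The sentences quoted are advice on extra care outside the study for subjects who go without. This stands. A reader might infer that the protocol expects some subjects to be off NA. It does not: it allows for the case and gives no number.

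**The main rebound endpoint is protected.** A reader might infer that off-NA rebounds will be counted as breakthrough on NA. The SAP note says otherwise, and the failure endpoint built on breakthrough follows it. The proportions with viral, biochemical and clinical relapse are specified by treatment group and HBeAg status, so follow-up type reaches them only through the general sentence in SAP 5. This stands too, subject to the missing definition of on NA. What remains exposed is chiefly the descriptive HBV DNA and HBsAg summaries and the laboratory and adverse event displays.

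**The monotherapy arms are not clearly the worst affected.** That inference is tempting because NA must be newly started there. Under Amendment 4, however, all Arm 1 subjects were to start NA on entering follow-up, Arm 6 subjects in the extension take NA from Week 24, and one breakthrough in Arm 6 adds NA for all remaining subjects in that arm. The documents do not support a ranking of arms.

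**NA intake can be traced.** SAP 4.6 lists NA administrations by subject, SAP 4.4 tabulates and lists anti-HBV NA medication, and viral markers are listed and plotted individually. It would therefore be too strong to say that off-NA events are hidden. Listings do not correct a summary table whose column heading is wrong, so the point survives in its narrower form.

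**Conclusion.** The point holds in a limited form. The SAP 2.3 rule mislabels any subject who misses the completion criteria and takes no NA, and the protocol explicitly allows for such subjects. The efficacy summaries and the laboratory and adverse event displays inherit the label. Breakthrough and the failure endpoint built on it are largely protected, but on NA is undefined, and off-NA rebound without the criteria met belongs to no failure category.

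The size is unknown. It is zero if every such subject takes NA, and otherwise proportional to the share who do not. The illustrative figures rest on assumed values and are not estimates. A reader might go further and infer that the tables will make NA look as if it fails after JNJ-56136379. The documents do not support that, since it depends on a share and on rates that they do not give.

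The primary endpoint, HBsAg change at Week 24, is on treatment and unaffected, and the study is exploratory. This is a correction worth making before follow-up tables are produced, not a threat to the main result.

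**What to change.** In SAP 2.3, derive follow-up status from NA start and stop dates in the exposure and concomitant medication data, with three levels: (1) treatment free after meeting Protocol Section 6.3; (2) on NA; (3) criteria not met and off NA.

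Assign each follow-up HBV DNA, HBsAg, ALT and adverse event record by NA status at the time of that record. A single class per subject is not enough: someone who starts NA late, after a flare, would be classed as on NA and the earlier off-NA flare would go with them. Show level 3 separately from NA follow-up in the efficacy, laboratory and adverse event displays. Use the same definition of on NA in the breakthrough note, and state where rebound in level 3 is reported, since neither post-treatment failure definition covers it.

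The change is analytical only and needs no new data. It costs one more derivation and one more display level, and the level 3 cells will be small.
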